#### 5.3.2 Ocular Assessments

Ocular data will be collected at screening visit, at week 24, 52, 76, 104 (EOT) visits. If two or more assessments performed within a time window, then the assessment closest to the planned visit is used in analyses by time window. When two values are equidistant from the planned assessment, the later one is used in analyses. The windowing defined is applicable for both on-treatment & post-treatment time periods. For the summaries by time point, we will be presenting the time points as defined below (Table 5-3).

For worst post-baseline assessment, all on-treatment values and post treatment values are considered regardless of time windows.

Table 5-4 shows the defined time windows.

Time point (Weeks)	Study Day	Lower Limit (day)	Upper Limit (day)
Baseline (Screening)	1*	-30	1
Week 24	162	2	259
Week 52	358	260	441
Week 76	526	442	623
Week 104	722	624	819

Table 5-4 Time windows for Ocular data

**End of Treatment -** Data collected at the EOT visit if conducted within 30 days of EOT date on disposition (DS) page in CRF.

For the post-baseline assessments among discontinued subjects, if no data were collected at the EOT visit the last available post-baseline on-treatment data will be used for EOT.

**\*Study Day 1** = first day of study treatment

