4.3 Definition of end of study

The end of study (EOS) will be when the latest of the following will have occurred:

- A) All patients completed 24 months of treatment, and patients completed their EOT visits and 30-day safety follow-up; OR
- B) Patients who discontinued from treatment prior to 6 months, or after 6 months but did not agree to participate in Post-treatment ocular follow-up: patients completed their EOT visits and 30-day safety follow-up; OR
- C) Patients who discontinued from treatment after 6 months and agreed to Post-treatment ocular follow-up: patients completed their EOT visits, 30-day safety follow-up, and Post-treatment ocular follow-up up to Month 24.

After completing the study or discontinuing from study treatment, patients will receive standard of care. The primary analysis will be based on the final locked data and will be summarized in the clinical study report (CSR).

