7.1 Study flow and visit schedule

Table 7-1 lists all assessments and indicates with an "X" the visits when they are performed. All data obtained from these assessments must be supported in the patient's source documentation.

Scheduled assessments should be done on the designated day, or as close to it as possible, i.e., not exceeding ± 3 days for assessments scheduled at Week 2 and Week 4, not exceeding ± 7 days for monthly visits until Week 104 (End of Treatment Visit), and not exceeding ± 30 days for assessments done approximately every 6 months, such as ocular and ECG assessments. In this clinical trial, a week is 7 calendar days, and 1 month is 30 days.

FRANCE SPECIFIC ONLY: The additional assessments of creatinine and creatinine clearance at Week 1 and Week 3 after start of treatment, and weekly checks of creatinine and creatinine clearance during the first month of dose increases, are specific to patients enrolled in sites from France. These assessments are NOT included in the Table 7-1, and should be recorded as unscheduled visits.

No eCRF will be used as a source document.

	Category	Protocol Section	Screening		Randomization								Treatment Period					End of study treatment (EoT)	30-day Follow up	Post-treatment Follow-up *
Weeks			-4	-2	Day 1	2	4	8	12	16	20	24	28, 32, 36, 40, 44, 48	52	56, 60, 64, 68, 72	76	80, 84, 88, 92, 96, 100	104	108	
Informed Consent	D	7.1.2	Х																	
IRT Registration	S	7.1.2.1	Х																	
Demography	D	7.1.2.3	Х																	
Inclusion/ exclusion	D	7.1.2	Х	Х																
HH history	D	7.1.2	х																	
Medical History	D	7.1.2.3	Х																	
Prior and concomitant medication / procedures	D	6.4	Con	tinuou	ısly till 30	day	s aft	er las	st dos	se of	study	treatr	nent							
Ocular History	D	7.1.2.3	Х																	

Table 7-1 Visit evaluation schedule

Novartis Amended Protocol Version 01 (Clean)

	Category	Protocol Section	Screening		Randomization								Treatment Period					End of study treatment (EoT)	30-day Follow up	Post-treatment Follow-up *
Weeks			-4	-2	Day 1	2	4	8	12	16	20	24	28, 32, 36, 40, 44, 48	52	56, 60, 64, 68, 72	76	80, 84, 88, 92, 96, 100	104	108	
Cirrhosis History	D	7.1.2	Х																	
Randomization	D	6.5			х															
Disposition	D	7.1.2		X														Х		Х
Molecular Testing of HH	D	7.2.2.6.1	X																	
Physical examination	S	7.2.2.1	Х		x	х	Х	х	Х	Х	х	Х	x	х	Х	Х	Х	Х		
Vital signs	D	7.2.2.2	Х		Х	Х	Х	Х	Х	Х	х	Х	Х	Х	Х	х	х	Х		

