10.8 Sample size calculation

The primary objective of the study is to estimate response rates and therefore the sample size is not based on power calculations. Sample size calculations were performed for the deferasirox FCT and phlebotomy arms to estimate the response rate (RR) with reasonable accuracy (half-width of 95% confidence interval).

Based on the Exjade study ICL670A2202, the patient dropout rate at month 6 (core study) is 24% and 12% at month 12 (optional extension phase). Assuming decreasing dropout rate over time and expected better patient compliance with deferasirox FCT formulation, a sample size of 100 patients in the FCT arm is expected to have at least 60 patients followed for 24 months to fulfil the FDA post-marketing requirement with regard to the ocular toxicity assessment in patients receiving deferasirox.

With a sample size of 100 on deferasirox FCT and 50 patients on phlebotomy, the projected half-widths of the 2-sided 95% confidence interval assuming various response rates are displayed in Table 10-3. The 95% confidence interval half-width extends at most to 0.096 and 0.136 in the deferasirox FCT and phlebotomy arms, respectively.

phiebotomy arms			
Response rate (RR)	Half-width of the 95% CI for deferasirox FCT N=100	Half-width of the 95% CI for phlebotomy N=50	
0.60	0.096	0.136	
0.65	0.093	0.132	
0.70	0.090	0.127	
0.75	0.085	0.120	
0.80	0.078	0.111	
0.85	0.070	0.099	
0.90	0.059	0.083	

Table 10-3Half-width of 95% CI of response rates in deferasirox FCT and
phlebotomy arms

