#### 4 Change to protocol specified analyses

Additional analysis related to COVID-19 related AEs and COVID-19 specific protocol deviations (Section 2.2.1 and Section 2.6.3) added. Due to COVID-19, the scheduled assessments had delays and consequently the subjects' assessments were unscheduled. Therefore, the Ocular windowing for the scheduled assessments was updated (see details in Section 5.3.2).

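### The Week 24 ocular window opens on Day 2, so an early stopper's end-of-treatment eye exam is normally tabulated as a month-6 result

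*SAP*

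**What the plan says.** SAP 5.3.2, Table 5-4, sets the Week 24 row (time point, planned day, lower limit, upper limit) as "Week 24 162 2 259". The later windows are Days 260-441 (Week 52, planned Day 358), 442-623 (Week 76, Day 526) and 624-819 (Week 104, Day 722). Day 1 is the first day of study treatment.

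Three rules in that section decide which exam fills a window:

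- Selection: "If two or more assessments performed within a time window, then the assessment closest to the planned visit is used in analyses by time window".
- Scope: "The windowing defined is applicable for both on-treatment & post-treatment time periods".
- Source: "Ocular data will be collected at screening visit, at week 24, 52, 76, 104 (EOT) visits". The completers' Week 104 exam is thus itself an EOT exam.

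A separate End of Treatment time point takes exams done within 30 days of the EOT date. Nothing says that an exam used there is kept out of the visit windows.

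SAP 4 gives the reason for updating the ocular windows: "Due to COVID-19, the scheduled assessments had delays and consequently the subjects' assessments were unscheduled". Protocol 7.1 allows no more than ±30 "days for assessments done approximately every 6 months, such as ocular and ECG assessments".

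On early stoppers, protocol 4.1.1 makes an eye exam part of the EOT visit when a patient stops between scheduled exams, and Table 7-1 marks the eye exams in its EOT column. Further ocular follow-up is offered only to patients with at least 6 months of assessments. Protocol 4.3 item B covers "Patients who discontinued from treatment prior to 6 months, or after 6 months but did not agree to participate in Post-treatment ocular follow-up" and lists only the EOT visit and the 30-day safety follow-up for them.

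**The concern.** Change from baseline at months 6, 12, 18 and 24 in visual acuity, intraocular pressure, lens and fundus findings is a named secondary objective, in a study run partly to meet an FDA ocular-safety requirement. A month-6 row should describe eyes after roughly six months.

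Under Table 5-4, a patient who stops in week 3 and has the EOT exam then is shown at month 6. No later exam competes, so the closest-exam rule cannot displace it. SAP 2.6.2 also tabulates completed ocular assessments by time point, so the same exam counts as a completed Week 24 assessment and overstates month-6 follow-up. COVID-19 delay makes exams late. It can explain generous upper limits, but not a lower limit of Day 2.

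**Working it through.** **1. Reproduce Table 5-4.** Planned day = (week − 1) × 7 + 1:

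- Week 24: 23 × 7 + 1 = 162
- Week 52: 51 × 7 + 1 = 358
- Week 76: 75 × 7 + 1 = 526
- Week 104: 103 × 7 + 1 = 722

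All four match the table. The midpoints between neighbouring planned days are (162 + 358)/2 = 260, (358 + 526)/2 = 442 and (526 + 722)/2 = 624. These are exactly the lower limits of Weeks 52, 76 and 104.

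| Time point | Window | Width (days) | Days before planned | Days after planned |
|---|---|---|---|---|
| Week 24 | 2-259 | 258 | 160 | 97 |
| Week 52 | 260-441 | 182 | 98 | 83 |
| Week 76 | 442-623 | 182 | 84 | 97 |
| Week 104 | 624-819 | 196 | 98 | 97 |

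The Week 24 lower limit is the exception. It reproduces only as the baseline upper limit plus one (1 + 1 = 2). The midpoint rule gives (1 + 162)/2 = 81.5, so Day 82, which is 80 days later than the stated limit. The protocol's −30 days gives 162 − 30 = Day 132, or Day 139 if Week 24 is counted as 24 × 7 + 1 = 169.

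**2. Follow an early stopper through the rules.** Take a patient who stops on Day 21 and has the EOT eye exam that day. Day 21 lies in 2-259. With fewer than 6 months of assessments, the patient is not offered ocular follow-up. Protocol 7.2.2.5 has follow-up exams recorded at Weeks 52, 76 and 104, not Week 24. The Day 21 exam is therefore the only candidate for Week 24 and is selected. It also meets the End of Treatment definition, so it is shown twice.

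**3. How many patients.** Inputs:

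- N = 100 on deferasirox (protocol 10.8).
- Dropout of 24% by month 6, the figure quoted in protocol 10.8 from the earlier dispersible-tablet study. A lower value of 10% is assumed here because the protocol expects better compliance with the film-coated tablet.
- Month 6 = 6 × 30.4375 = 182.6 days (SAP month length).
- Assumed: every stopper has an EOT eye exam on the day of stopping.

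Even timing: number before Day 82 = 100 × d × 81/182.6.

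- d = 0.24: 24 × 81/182.6 = 10.6
- d = 0.10: 10 × 81/182.6 = 4.4

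Constant hazard: 100 × [1 − (1 − d)^(81/182.6)] gives 11.5 and 4.6. Within the first 28 days, even timing gives 24 × 28/182.6 = 3.7 and 10 × 28/182.6 = 1.5.

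**4. What a Day 82 start leaves.** At 24% and even timing, 24 − 10.6 = 13.4 values from patients who stopped before month 6 remain, out of 100 − 10.6 = 89.4 (about 15%). Of these, 24 × (131 − 81)/182.6 = 6.6 fall on Days 82-131. The other 6.8 fall on or after Day 132, where the protocol's own tolerance around Day 162 begins.

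**The case against.** **Early stoppers may have a later exam.** Protocol 7.1.5 says patients who discontinue treatment are not withdrawn and should return for the assessments in 7.2.2.5, without a 6-month condition. An exam near Week 24 would then displace the early one. But 7.2.2.5 ties continued exams to patients eligible for ocular follow-up, and 4.1.1 and 4.3 point the same way, so this does not remove the problem.

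**Early stoppers may have no exam.** Protocol 7.2.2.5 describes the between-visit EOT exam for follow-up-eligible patients. Section 4.1.1 and the EOT column of Table 7-1 are not limited in that way. If sites followed the narrower reading, or patients were lost or withdrew consent, fewer values are affected. This stands, and it makes the counts above upper-end figures for the assumed dropout rates.

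**The consequences are limited.** All ocular analyses are descriptive. By-visit tables deliberately combine on- and post-treatment exams, swimmer plots show dosing, listings are planned, and an End of Treatment row exists. Windows without gaps that keep every exam are a common choice. This stands as a limit on severity. It does not justify a month-6 label on a week-3 exam, since the same exam is retained elsewhere.

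**Stronger readings that the documents do not support.** A reader might infer that untreated patients enter the month-6 table. They do not: the ocular tables use the Safety Set, which requires at least one administration. A reader might also infer that month-6 effects are understated by up to 24%. That figure is another formulation's dropout, assumes an exam for every stopper, and counts patients treated almost to Week 24. Nor is the direction certain, because a patient who stops for an eye problem brings an abnormal exam into Week 24. No phlebotomy dropout rate is given, so an imbalance between arms cannot be sized.

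**Conclusion.** The point holds as a cheap improvement. As written, the EOT eye exam of a patient who stops early normally fills Week 24, however short the exposure, and is repeated under End of Treatment. It affects the by-time-point ocular summaries at month 6 and the counts of completed Week 24 assessments, in both arms. Dilution of month-6 change is likely but not assured.

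The size rests on assumptions about dropout, its timing and EOT attendance: about 4 to 11 of 100 deferasirox Week 24 values from before Day 82. The key secondary ocular adverse event incidence (SAP 2.5) and the worst post-baseline tables do not use these windows, so it would be wrong to conclude that the main ocular safety result is compromised.

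**What to change.** In SAP Table 5-4, change the Week 24 lower limit from Day 2 to Day 82, the midpoint of Day 1 and Day 162. Add to 5.3.2 that an EOT exam enters a visit window only if its date falls inside that window, and that earlier exams are shown only in the End of Treatment row, the listings, the swimmer plots and the worst post-baseline tables. The completers' EOT exam stays in Week 104. While editing, correct the sentence in 5.3.2 that points to Table 5-3 for the ocular time points; Table 5-4 is meant.

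The cost is one number and a sentence or two. The Week 24 tables would have slightly fewer patients, and no data are lost. Some early stoppers examined from Day 82 onwards would remain, as in the other windows.

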7.1.2 Screening

Prior to screening, the patient must give full informed consent on the appropriate form. Once signed and dated by the patient, the investigator must review the study's inclusion and exclusion criteria with the patient to ensure that the patient is eligible to participate.

Two Screening Visits (at -4 weeks and at -2 weeks) are needed to perform key safety parameters prior to first dose administration per the deferasirox drug label and to confirm eligibility criteria.

Molecular testing of HH must be performed at the first screening visit if historical diagnosis is not available.

Specific safety assessments including ophthalmic and audiometry examinations, ECG, and cirrhosis assessment (unless diagnosis is available during the past 12 months, or SF is <1000 μ g/L and AST/ALT are normal) must be performed prior to starting study drug. It is preferred that they are performed at the first screening visit (-4 weeks), but to make it possible for the site to plan the examinations properly, these assessments can be performed at the second screening visit (-2 weeks).

SF, serum creatinine and urine protein/creatinine ratio will be measured at both screening visits and used to assess eligibility. SF should be obtained in the absence of any infection or inflammation.

Serum Pregnancy test will be required for females of child-bearing potential only.

The full list of assessments to be performed during screening is detailed in Table 7-1.

Re-screening is permissible on a case-by-case basis. All assessments at screening visits must be repeated if a patient is re-screened, except for molecular testing of HH, Ocular, Audiometry, ECG, and cirrhosis assessments. Please contact Novartis for guidance and see Section 7.1.2.2 on how to process screen failures.

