#### Date of First/Last Administration of Study Treatment

For Deferasirox FCT:

- The date of first administration of study treatment is derived as the first date when a non-zero actual dose of study treatment was administered as recorded on Dose Administration Record (ZQ) Electronic Case Report Form (eCRF).
- The date of last administration of study treatment is defined as the last date when a nonzero actual dose of study treatment was administered as recorded on ZQ eCRF.

For Phlebotomy:

- The date of first administration of study treatment is derived as the first date when a non-zero volume of blood removed was recorded on Phlebotomy Record eCRF (FAZU) on or after the randomization date.
- The date of last administration of study treatment is defined as the last date when a nonzero volume removed of blood was recorded on Phlebotomy Record eCRF (FAZU). This date will also be referred as 'last date of study treatment'.

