#### Baseline

Baseline is considered as the result of an investigation describing the 'true' uninfluenced state of the subject.

For **efficacy evaluations**, (e.g. serum ferritin), the last available assessment before or on the date of randomization is taken as 'baseline' value or 'baseline' assessment.

For **safety evaluations** (e.g. laboratory, vital signs, ocular etc.) the last available assessment before or on the date of start of study treatment is taken as 'baseline' value or 'baseline' assessment.

If subjects have no value as defined above, the baseline result will be missing.

If an assessment is planned to be performed prior to the first administration of study treatment in the protocol and the assessment is performed on the same day as the first administration of study treatment, it will be assumed that it was performed prior to study treatment administration if assessment timepoint is not collected or is missing. Unscheduled assessments will be considered in the determination of baseline.

Subjects who start treatment and discontinue from the study on the same day may have 2 different sets of data collected on study Day 1, one being reported to the Day 1 visit, the other reported to the EOT visit. Data reported at the EOT visit are not eligible for baseline selection.

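### The SAP gives two conflicting rules for the ocular baseline, and the Day -30 limit in Table 5-4 can exclude screening exams that the protocol accepts

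*SAP*

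**What the plan says.** **General rule.** SAP 2.1.1 (Baseline) lists ocular data among the safety evaluations. For these, "the last available assessment before or on the date of start of study treatment is taken as 'baseline' value". No earliest day is given, and unscheduled assessments count. It adds: "If subjects have no value as defined above, the baseline result will be missing".

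**Ocular table.** SAP 5.3.2, Table 5-4, has a row labelled "Baseline (Screening" with lower limit -30 and upper limit 1. Its footnote defines Study Day 1 as the "first day of study treatment". The laboratory table (Table 5-3) sets no lower limit for baseline.

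**When treatment starts.** In the phlebotomy arm it is the first date on which a "non-zero volume of blood removed was recorded on Phlebotomy Record eCRF (FAZU) on or after the randomization date" (SAP 2.1.1). No maximum delay is stated. Protocol Table 7-1 has deferasirox dispensed at the randomisation visit.

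**When the exam is done.** Protocol 7.1.2 covers the ophthalmic, audiometry, ECG and cirrhosis assessments: "It is preferred that they are performed at the first screening visit (-4 weeks"). The second screening visit, at Week -2, is allowed. On re-screening, screening assessments are repeated "except for molecular testing of HH, Ocular, Audiometry, ECG, and cirrhosis assessments".

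**The concern.** The two rules select different baselines for the same patient whenever the only pre-treatment ocular exam is earlier than Day -30. Nothing in the SAP ranks one above the other. Section 2.1.1 is explicit about ocular data. Section 5.3.2 is the specific ocular section, and SAP 2.1.1 (On-treatment Period) and 2.6.2 both send the reader there for detail. SAP section 4 attributes the updated ocular windows to COVID-19 delays in scheduled assessments and does not say that the baseline definition changed.

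Table 5-4 also counts from first treatment, whereas the protocol schedules visits from randomisation. An exam at the preferred visit therefore has little slack before it falls outside the window.

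A patient without a baseline drops out of every ocular change-from-baseline, shift and worst-change summary in SAP 2.6.2. Those summaries address a stated secondary objective, and the planned control arm is only 50 patients.

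**Working it through.** **Inputs**
- Baseline window, Day -30 to Day 1 from first treatment: SAP Table 5-4.
- Study day before treatment = assessment date minus treatment start date: SAP 2.1.1 (Study Day).
- Week = 7 days: Protocol 7.1. Visits counted from randomisation: Protocol 7.1.4.
- Exam at Week -4 (28 days before randomisation) or Week -2 (14 days before): Protocol 7.1.2.
- Gap *g*, in days from randomisation to first treatment: not given in the documents, so varied below.

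**Reproducing Table 5-4**
- Planned day = (week - 1) × 7 + 1. Weeks 24, 52, 76 and 104 give 162, 358, 526 and 722, as printed.
- Upper limit = midpoint to the next planned day, minus 1: (162 + 358)/2 - 1 = 259; (358 + 526)/2 - 1 = 441; (526 + 722)/2 - 1 = 623. For the last window, 722 + 98 - 1 = 819. All match.
- The -30 limit follows from no such rule, and the SAP gives no derivation for it.

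**When an exam falls outside the window**

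Study day of exam = -(days before randomisation + *g*). It is outside when this is below -30.
- Week -4 exam: 28 + *g* > 30, so *g* ≥ 3. At *g* = 0 it is Day -28, with 2 days of slack; at *g* = 3 it is Day -31.
- Week -2 exam: 14 + *g* > 30, so *g* ≥ 17.
- Treatment started on the day of randomisation (*g* = 0): only exams done 31 or more days before randomisation are outside. An unrepeated exam from an earlier screening can be that old, in either arm.

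**Illustrative loss if Table 5-4 selects the baseline**

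Gaps are assumed to be uniform over whole days, and each exam to fall exactly on its nominal day.

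| Assumed gap (days) | Week -4 exam lost | Week -2 exam lost |
|---|---|---|
| 0-2 | 0/3 = 0% | 0% |
| 0-6 | 4/7 = 57% | 0% |
| 0-7 | 5/8 = 62.5% | 0% |
| 0-13 | 11/14 = 79% | 0% |
| 0-14 | 12/15 = 80% | 0% |

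If 2.1.1 selects the baseline, the loss is 0% in every row.

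**The case against.** The best reply is that the SAP already defines the ocular baseline. Section 2.1.1 names ocular data, and it makes baseline missing only when there is no value under its own definition. Section 5.3.2 introduces its time points for by-time-point summaries and never says that an exam before Day -30 is discarded. On that reading 2.1.1 picks the baseline, Table 5-4 only labels visits, and nothing is lost. This reading is reasonable, so the loss is a possibility and not a certainty. It does not remove the conflict, because the table prints a baseline window with a limit that 2.1.1 lacks and no sentence subordinates it.

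A reader might infer that the loss would fall mainly on the phlebotomy arm, since its Day 1 waits for the first recorded blood removal while deferasirox is dispensed at randomisation. The documents do not establish this. SAP 1.1 has both treatments beginning on Day 1. The protocol leaves the frequency of phlebotomy to the physician but does not say that its start may be deferred. No delay distribution is given. Greater exposure in that arm is plausible; its size is unknown. Re-screening can affect either arm and is allowed only case by case.

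A legitimate case also exists for capping the age of a baseline exam. If a cap is intended, the SAP should say so and reconcile it with 2.1.1.

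**Conclusion.** The SAP contradicts itself on the ocular baseline, and this should be settled before database lock. The effect is conditional: exams are lost only if Table 5-4, rather than 2.1.1, selects the baseline. The loss is then 0% for gaps of 0-2 days, or for Week -2 exams with gaps up to 16 days. It rises to roughly 57-80% of Week -4 exams under assumed uniform gaps of one to two weeks. Those percentages illustrate sensitivity and are not expected losses; they also assume every such exam falls exactly 28 days before randomisation.

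It would be tempting to read this as a threat to the key secondary endpoint. It is not: incidence of ocular AEs (SAP 2.5) does not use the exam window. Post-baseline by-visit counts of abnormalities and of intraocular pressure categories need no baseline either. The outputs at risk are the descriptive secondary change-from-baseline, shift and worst-change summaries, on which no hypothesis is tested.

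**What to change.** In SAP Table 5-4, replace the baseline lower limit of -30 with a rule of on or before Study Day 1, as the laboratory table already does. Add one sentence to 5.3.2 stating that the ocular baseline follows 2.1.1. In the ocular listings, flag baseline exams done more than 30 days before first treatment, so that their age is visible.

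The change is one table cell, one sentence and one listing flag, and it needs no new data. The downside is that a few baselines will be somewhat older than the printed window would allow.
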